**Table 8-7 Overview of Effectiveness Analysis**

Outcome	Primary/Secondary	Statistical Method 1	Statistical Method 2	Statistical Method 3
Annual HV	Primary	MMRM, 95% CI	MMRM + IPTW, 95% CI	Descriptive stats
Height standard deviation score (SDS) and change in height SDS	Primary	MMRM, 95% CI	MMRM + IPTW, 95% CI	Descriptive stats
HVSDS	Primary	MMRM, 95% CI	MMRM + IPTW, 95% CI	Descriptive stats
Change in annual BMI	Primary	MMRM, 95% CI	MMRM + IPTW, 95% CI	Descriptive stats
Change in annual BMI SDS	Primary	MMRM, 95% CI	MMRM + IPTW, 95% CI	Descriptive stats
Change in Bone age	Primary	MMRM, 95% CI	MMRM + IPTW, 95% CI	Descriptive stats
Change in IGF	Primary	MMRM, 95% CI	MMRM + IPTW, 95% CI	Descriptive stats
Change in IGF-I SDS	Primary	MMRM, 95% CI	MMRM + IPTW, 95% CI	Descriptive stats

090177e1a57a0182\Approved\Approved On: 16-Feb-2026 13:43 (GMT)

[1] Continuous variables will be summarized using descriptive statistics which will include the number of patients with data to be summarized (n), mean, standard deviation (SD), median, first and third quartiles (Q1, Q3), minimum, maximum, and the number of missing observations. Descriptive statistics for categorical/qualitative variables will be presented with number of patients (count) and percentage and this will be presented in the format 'n (%)'.

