**Repeated Measures**

This model will only be performed with those patients without treatment switch until a given time point. Continuous variables will be analyzed by a Mixed Model for Repeated Measures (MMRM) under the MAR framework, including all post baseline timepoints data as outcome variables and baseline data as a covariate including the relevant patient/disease characteristics. Repeated time variable will be modeled as a continuous variable and treatment (Genotropin versus Ngenla) as a class variable with an unstructured covariance and least square means along with 95% CI will be presented.

The adjusted mean changes from Baseline at Month 6, 12, 18, 24, etc., for each treatment group will be estimated in the framework of this model, as well as the between group differences and the 95% CIs for the adjusted mean, when applicable.

The MMRM model will be implemented using SAS® (version 9.4 or higher) generalized linear mixed procedure (PROC MIXED) with an unstructured correlation matrix to model the within-patient errors. If this model does not converge, a heterogeneous Toeplitz covariance structure followed by the

090177e1a57a0182\Approved\Approved On: 16-Feb-2026 13:43 (GMT)

heterogeneous first-order autoregressive covariance structure will be considered. Parameters will be estimated using the Newton-Raphson algorithm. Denominator degrees of freedom will be estimated using the Kenward-Roger approximation.

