### **Longitudinal Model/Sensitivity Analysis**

To assess the longitudinal association between outcomes and time-varying treatment (*i.e.* patients switch treatment from Genotropin to Ngenla or vice versa at any time-point), a propensity model approach will be applied to calculate the inverse probability of treatment weights (IPTW). This model is assumed to control for time-varying confounding when time-varying treatments are used in longitudinal analyses.

The IPTW will be calculated using propensity score model in which the choice of the treatment at each visit will be considered as the outcome (Genotropin vs Ngenla) and the pre-specified baseline characteristics (See Table 9-3 Model Covariates) as independent variables. Once IPTWs per patient are derived, the models described in the Repeated Measure model will be applied with the weights. The models will include treatment group (time-varying covariate), time (in years) and IPTW. This approach will be considered as a sensitivity analysis *to assess the impact of treatment switching*.

Detailed methodology for summary and statistical analyses of data collected in this study will be documented in a statistical analysis plan (SAP), which will be dated, filed, and maintained by the sponsor. The SAP may modify the plans outlined in the protocol; any major modifications of primary endpoint definitions or their analyses would be reflected in a protocol amendment.

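### The IPTW sensitivity analysis for switching changes the confounding control as well as admitting switchers, so its difference from the MMRM cannot be attributed to switching

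*Protocol*

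**What the plan says.** Protocol section 8.7 describes two models for the continuous effectiveness outcomes.

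- **Repeated Measures.** The population is restricted: "This model will only be performed with those patients without treatment switch until a given time point". Confounding is handled by regression, with "baseline data as a covariate including the relevant patient/disease characteristics". Treatment enters as a fixed group: "treatment (Genotropin versus Ngenla) as a class variable with an unstructured covariance". No weights are used.
- **Longitudinal Model/Sensitivity Analysis.** This covers the case in which "patients switch treatment from Genotropin to Ngenla or vice versa at any time-point". A propensity model for treatment at each visit, built on the baseline characteristics of the model-covariates table, yields the weights. Then: "Once IPTWs per patient are derived, the models described in the Repeated Measure model will be applied with the weights". The listed model contents are time-varying treatment, time in years and IPTW. Of the whole, the protocol says "This approach will be considered as a sensitivity analysis" and gives its purpose as assessing what treatment switching does.

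Table 8-7 (Overview of Effectiveness Analysis) and its counterpart in the abstract list MMRM as Method 1 and "MMRM + IPTW, 95% CI" as Method 2 for all eight effectiveness rows. Neither states a population for either method. The third method is descriptive statistics.

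**The concern.** A sensitivity analysis of switching is informative when set against an analysis that differs from it only in how switching is treated. Here the comparator differs in two respects: whether switchers contribute, and whether confounding is controlled by covariate adjustment or by weighting. The second difference matters in itself. When the treatment effect is not the same in all patients, the two methods average it with different weights over patient types. They also fail differently when the outcome model is misspecified.

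Two misreadings are possible. If the estimates disagree, the reader may conclude that switching distorts the comparison when the change of method produced the gap. If they agree, two opposite differences may have cancelled. In addition, the MMRM in non-switchers gets no clearly planned weighted check in its own population.

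**Working it through.** The protocol gives no figure on this point, so there is none to reproduce. The check has three parts.

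**1. The two specifications side by side**

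| Feature | Repeated Measures MMRM | Longitudinal IPTW model |
|---|---|---|
| Patients | No switch up to the time point | Switchers contribute |
| Treatment term | Fixed group | Time-varying |
| Confounding control | Baseline value and patient/disease covariates, unweighted | Inverse probability weights from a visit-level propensity model |
| Outcome-model covariates | Yes | Unclear: not among the listed terms, but the text also says the repeated-measures models are applied with weights |

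The first two rows together are the switching change. The third is a separate change, and the fourth may be one. Neither possible bridge is described: the weighted model without switchers, or the unweighted adjusted model with them.

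**2. Two-stratum algebra with no switchers**

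From the protocol: 700 Ngenla and 2000 Genotropin participants (section 8.5), and a pivotal-trial difference of 10.10 − 9.78 = 0.32 cm/year (section 6). Assumed, and not in the protocol: GH-naive patients split 400 Ngenla / 400 Genotropin with a true effect of 0.8 cm/year, and non-naive patients split 300 / 1600 with an effect of 0.

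Covariate adjustment with a common treatment effect weights each stratum by n·p·(1 − p), where p is the Ngenla share:

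- Naive: 400 × 400 / 800 = 200
- Non-naive: 300 × 1600 / 1900 = 252.6
- Estimate: 0.8 × 200 / (200 + 252.6) = 0.353 cm/year

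IPTW weights each stratum by its size n:

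- Estimate: 0.8 × 800 / 2700 = 0.237 cm/year

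The gap is 0.353 − 0.237 = 0.116, about 0.12 cm/year. Relative to the pivotal difference this is 0.116 / 0.32 = 36%. Nobody in this example switches.

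**3. Simulation with no switchers**

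Settings: N = 2700, 26 to 28% on Ngenla, 200 replicates each, one outcome per patient, true average difference 0.32 cm/year. All else is assumed: one standardised baseline covariate; log-odds slope of treatment on it of 0, 0.5 or 1; effect modification of 0, 0.2 or 0.4 cm/year per SD; a quadratic term of 0 or 0.2 that the adjusted model omits; residual SD 2.

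| Slope | Effect modification | Quadratic term | Adjusted, unweighted | IPTW | Gap |
|---|---|---|---|---|---|
| 0 | any | any | 0.31 to 0.33 | 0.31 to 0.33 | 0.00 |
| 0.5 or 1 | 0 | 0 | 0.32 | 0.32 | 0.00 |
| 0.5 | 0 | 0.2 | 0.34 | 0.31 | −0.02 |
| 0.5 | 0.4 | 0 | 0.41 | 0.32 | −0.09 |
| 1 | 0.4 | 0 | 0.47 | 0.32 | −0.15 |
| 1 | 0.4 | 0.2 | 0.55 | 0.32 | −0.23 |

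Gaps were computed before rounding. Wherever treatment choice depended on the covariate and either the effect varied with it or the outcome model was wrong, the gap lay between −0.02 and −0.23 cm/year. Keeping the covariate in the weighted model moved that estimate by at most 0.01 in these settings. The unclear fourth row above is therefore mainly a matter of specification here.

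The conditions for a gap are plausible in this study. The background describes Ngenla as approved for growth failure from inadequate endogenous GH, while daily hGH is used across several further indications. Section 8.7 itself plans subgroups by naive status, diagnosis and peak GH.

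**The case against.** Several counter-arguments have force.

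- **No attribution rule.** A reader might infer that the protocol defines the difference between the two models as the effect of switching. It does not. It names a purpose and sets no rule for reading the contrast. The analysis can be taken as a general robustness check, and no decision depends on it in a study described as descriptive. This stands, and it limits the severity. The stated purpose still concerns switching alone, and the analysis as planned cannot isolate that.
- **The weights have a reason.** The protocol introduces them to deal with time-varying confounding once treatment varies. Weighting is therefore not arbitrary, and this point does not call it the wrong method. The missing piece is a step between the two models.
- **A weighted model in non-switchers may be intended.** The text says "the models described in the Repeated Measure model will be applied with the weights", and the model so described is limited to non-switchers. Table 8-7 is silent on population. However, IPTW is introduced only for patients whose treatment changes, with treatment as a time-varying term, so the surrounding text favours the other reading. If both were meant, one label covers two analyses and the text needs correcting anyway.
- **The SAP may add supportive models.** It may. The protocol itself, though, fixes this single analysis and its purpose.
- **The numbers are constructed.** They are. The strata, effects and simulation settings are assumptions, and the planned naive/non-naive subgroup results would reveal that kind of heterogeneity for the height outcomes. The documents do not support a claim that a gap of any given size will occur.

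It would also go too far to say that the protocol labels the MMRM as primary. The tables label outcomes, not methods, as primary; the MMRM's leading role is only implied by calling the other model a sensitivity analysis.

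**Conclusion.** The point holds on the text. The two planned models differ in population and exposure and in confounding control, and possibly in outcome-model covariates, with no model in between. A difference between them cannot be attributed to switching, and agreement does not show that switching is harmless.

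The size is unknown. It is zero if treatment choice is unrelated to patient characteristics, or if the effect is constant and the outcome model correct. It was about 0.12 cm/year in the assumed strata and 0.02 to 0.23 cm/year in the affected simulation settings, all without switchers. These figures show only that a gap can arise without switching; they do not predict one. This is an inexpensive improvement to interpretability and does not show that either model is invalid.

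**What to change.** In section 8.7 and Table 8-7, and in the matching abstract table, add one bridging run per outcome: the planned IPTW model restricted to person-time without a switch. It should use the same propensity specification and the same outcome-model terms as the planned model, and the text should say whether the outcome-model covariates are kept. A bridge with a different propensity model, such as one for baseline treatment only, would again change two things at once when set against the full model.

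The comparisons then read as follows:

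- Bridging run against the unweighted MMRM: check on confounding control.
- Full IPTW model against the bridging run: check on including switchers. The text should note that visit-level weights built from baseline covariates alone may leave confounding of the switch itself.

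The same edit should state whether post-switch data enter at all, since section 8.2 ends follow-up at discontinuation of either product.

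If no run is added, the minimum is to reword the purpose as a joint robustness check of weighting and switching. The cost is one additional model run for each outcome in the eight rows of Table 8-7, plus the wording.

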## **8.8 Quality Control**

GloBE-Reg has a formalized process for quality/assurance of data. Data entered in the GloBE-Reg database will be formally assessed for quality on an annual basis; there is no hand-written data entry, therefore legibility is not a concern. Ten percent of cases (or a minimum of 1) included from each center shall be eligible for a remote quality assurance (QA), with cases selected using a randomization tool. For selected cases, the center lead clinician is invited to submit evidence through the QA platform that is built into the registry, and GloBE-Reg arranges a QC-specific meeting to discuss the process in detail. At a site level, investigators in respective countries are responsible for following their standard institutional procedures to ensure data quality and integrity.

In addition, the useability of the platform for data entry is checked through biannual user surveys. Internal validation protocols and required mandatory completion checks are performed. During subsequent processing and analysis, outliers and missing values are identified and reviewed. Data quality will be maximized through a range of other mechanisms, including data validation, data cleansing, data profiling and internal audits:

- Data Validation - Selected data fields have internal validation mechanisms and mandatory completion and outliers and missing values commonly become apparent and checked during

data processing and analysis. The data dictionary is automated, and the codes for specific data fields can be downloaded directly from the registry.

- Data Cleaning – The data is processed to check for duplicate records, inconsistencies, and inaccuracies at regular intervals.
- Data Profiling - Data is processed to understand its structure, patterns and relationships at regular intervals.

GloBE-Reg was developed based on the EMA Guideline on registry-based studies EMA/426390/2021 released on 22 October 2021 and follows Good Pharmacoepidemiology Practices and is approved by the National Research Ethics Service and Information Governance authorities in the UK.

The steering committee of GloBE-Reg established a working group of experts to create a minimum dataset for the registry. The group determined that this set consists of items that can be readily measured in a standard clinical setting worldwide to track the efficacy and safety of hGH, both long-acting and daily, in children with GHD.

Additionally, all information is stored on a secure server at the University of Glasgow in compliance with UK Data Protection Act (2018) and General Data Protection Regulation (GDPR 2016/679).

## 8.9 Limitations of the Research Methods

This is a non-interventional observational study, therefore, there are several potential limitations which are well-described in the literature for comparable studies, such as Kabi/Pfizer International Growth Database (KIGS) (13,14). As a retrospective cohort study, without randomization, there is a potential for variable quality and completeness of data. In addition, confounding and biases cannot be excluded, and determination of causation is limited. Enrollment or selection bias is possible since it is affected by the willingness or ability of physicians and patients to participate in GloBE-Reg. However, centers are expected to enroll all eligible patients treated with Ngenla (somatrogon) and Genotropin (somatropin). Follow-up bias is a potential limitation as well, especially if patients with AEs are less likely to return to the treating physician or center for follow-up.

Regarding the secondary endpoints on safety and adverse events, there is a potential risk of underestimating the safety outcomes due to underreporting, misreporting or missing data from the eCRFs, and/or EHR. The clinician entering data in the registry is responsible for evaluation of seriousness and causality of the safety and adverse events and due to the secondary collection of this data further investigation is limited.

Additional potential limitations specific to our study include:

- Data collection will reflect routine clinical practice rather than mandatory assessments at specified time points thereby increasing heterogeneity of the data. For this reason, visit windows (defined in the SAP) will be applied to the statistical analysis.
- The data source for this study is the subset of participants treated with either Ngenla (somatrogon) or Genotropin (somatropin) from the GloBE-Reg registry, which collects routine data from across the world and is reflective of different routine clinical practices according to region. This may lead to heterogeneity of the data and result in information bias. For this reason, subgroup analysis will be carried out for the primary efficacy

endpoints and pre-identified confounders will be included in the statistical models as presented in Table 9.3.

- Information bias may also occur related to risk of loss to follow up due to the long duration of this study or adverse event occurrence.

## 8.10 Other Aspects

Not applicable.

## 9. PROTECTION OF HUMAN PARTICIPANTS

### 9.1 Patient Information

This study involves data that exist in deidentified/anonymized structured format and contain no participant personal information.

### 9.2 Patient Consent

As this study involves deidentified/anonymized structured data, which according to applicable legal requirements do not contain data subject to privacy laws, obtaining informed consent from participants by Pfizer is not required.

### 9.4 Institutional Review Board (IRB)/ Ethics Committee (EC)

There must be prospective approval of the study protocol, protocol amendments, and other relevant documents (*e.g.*, informed consent forms if applicable) from the relevant IRBs/ECs. All correspondence with the IRB/EC must be retained. Copies of IRB/EC approvals must be forwarded to Pfizer.

### 9.5 Ethical Conduct of the Study

The study will be conducted in accordance with legal and regulatory requirements, as well as with scientific purpose, value, and rigor and follow generally accepted research practices described in:

- Guidelines for Good Pharmacoepidemiology Practices (GPP). Public Policy Committee, International Society of Pharmacoepidemiology. *Pharmacoepidemiology and Drug Safety* 2015; 25:2-10. [https://onlinelibrary.wiley.com/doi/full/10.1002/pds.3891\(15\)](https://onlinelibrary.wiley.com/doi/full/10.1002/pds.3891(15))
- Good Practices for Outcomes Research issued by the International Society for Pharmacoeconomics and Outcomes Research (ISPOR) [http://www.ispor.org/workpaper/practices\\_index.asp\(16\)](http://www.ispor.org/workpaper/practices_index.asp(16))
- Good practices for real-world data studies of treatment and/or comparative effectiveness: Recommendations from the joint ISPOR-ISPE Special Task Force on real-world evidence in health care decision making [https://www.ncbi.nlm.nih.gov/pmc/articles/PMC5639372/\(17\)](https://www.ncbi.nlm.nih.gov/pmc/articles/PMC5639372/(17))

- ❑ International Ethical Guidelines for Epidemiological Studies issued by the Council for International Organizations of Medical Sciences (CIOMS)  
<https://cioms.ch/shop/product/international-ethical-guidelines-for-epidemiological-studies/> □  
European Medicines Agency (EMA) European Network of Centres for Pharmacoepidemiology and Pharmacovigilance (ENCePP) Guide on Methodological Standards in Pharmacoepidemiology  
[http://www.encepp.eu/standards\\_and\\_guidances/methodologicalGuide.shtml](http://www.encepp.eu/standards_and_guidances/methodologicalGuide.shtml)(18)
- ❑ Food and Drug Administration (FDA) Guidance for Industry: Good Pharmacovigilance Practices and Pharmacoepidemiologic Assessment  
<https://www.fda.gov/downloads/drugs/guidancecomplianceregulatoryinformation/guidances/ucm071696.pdf>(19)
- ❑ FDA Guidance for Industry and FDA Staff: Best Practices for Conducting and Reporting Pharmacoepidemiologic Safety Studies Using Electronic Healthcare Data  
<http://www.fda.gov/downloads/Drugs/GuidanceComplianceRegulatoryInformation/Guidance/UCM243537.pdf>(20)
- ❑ European Medicines Agency. Guideline on good pharmacovigilance practices (GVP) Module VIII - Post-authorisation safety studies (EMA/813938/2011 Rev 3). 2017(21)

## 10. MANAGEMENT AND REPORTING OF ADVERSE EVENTS/ADVERSE REACTIONS

This study involves data that exists as structured data by the time of study start.

In these data sources, individual patient data are not retrieved or validated, and it is not possible to link (*i.e.*, identify a potential association between) a particular product and medical event for any individual. Thus, the minimum criteria for reporting an adverse event (AE) (*i.e.*, identifiable patient, identifiable reporter, a suspect product, and event) cannot be met.

## 11. PLANS FOR DISSEMINATING AND COMMUNICATING STUDY RESULTS

One or more abstracts may be developed and submitted to relevant scientific conference(s) and one or more manuscripts may be developed and submitted to relevant peer-reviewed medical journals. Authorship will follow the guidelines proposed by the International Committee of Medical Journal Editors (ICMJE; [www.icmje.org](http://www.icmje.org)). All authors should meet the criteria for authorship, and all people who meet the criteria should be authors. Any potential conflicts of interest will be disclosed. Additionally, annual investigator meetings are planned to disseminate data and communicate study results.

In the event of any prohibition or restriction imposed (eg, clinical hold) by an applicable competent authority in any area of the world, or if the party responsible for collecting data from the participant, is aware of any new information which might influence the evaluation of the benefits and risks of a Pfizer product, Pfizer should be informed immediately.

The final clinical study report will be submitted to EMA according to Article 46 of the **Paediatric** Regulation (EC) No. 1901/2006.

### 14. LIST OF FIGURES

Not Applicable

